#### Abstract

Background and Rationale: Headaches following mild traumatic brain injury (mTBI) are common, can be refractory to standard therapies, and may persist and worsen to become a debilitating chronic pain syndrome. The purpose of this study is to evaluate the centrally acting alpha-1 adrenoreceptor (AR) antagonist drug prazosin as a prophylactic treatment for chronic posttraumatic headaches (PTHAs). The impetus for this study comes from a large open-label case series in Iraq and Afghanistan Veterans with mTBI and PTHAs and data from a placebo-controlled trial evaluating use of prazosin for posttraumatic stress disorder (PTSD) in active-duty Service Members (SMs). Findings from these studies showed that in addition to decreasing PTSD-related symptoms and improving sleep quality, prazosin decreased the frequency and severity of headaches, which were common in the study populations.

Study Objectives, Specific Aims, and Hypotheses: The objective of this study is to evaluate the efficacy of prazosin as a prophylactic treatment for persistent PTHAs, which will be accomplished by conducting a randomized placebo-controlled double blind trial of prazosin vs. placebo in active-duty SMs and Veterans.

*Specific Aim 1*: To determine the effect of prazosin compared to placebo on headache frequency, headache severity and duration, use of abortive/analgesic medications, and headache-related disability.

*Specific Aim 2:* To determine the effect of prazosin on sleep disturbance, PTSD symptoms, depressive symptoms, alcohol consumption, global cognitive function, health-related quality of life, and global clinical status.

Study Design: The study design is based on International Headache Society (IHS) guidelines for prophylactic treatment trials for migraine. The study will enroll 228 active-duty SMs and Veterans. Total trial length will be up to 24 weeks, including a 4-week headache screening period, a 1-week screening sleep monitoring period, a 5-7 week dose titration period, and a 12-week steady-dose study drug period, for which participants will be randomized 2:1 to prazosin or placebo. Headache characterization and quantitative assessment of sleep quality, PTSD symptoms, mood, alcohol/substance use, cognition, health-related quality of life, and headache-related disability assessments will be performed at baseline and at 4-week intervals during the steady-dose period. Participants will keep a daily headache log for the duration of the trial. The primary outcome measure will be change from baseline in headache frequency. Secondary outcome measures will include change in other headache measures, sleep quality, PTSD symptoms, mood, alcohol, cognition, quality of life, and headache-related disability. Data will be analyzed using standard statistical techniques.

Clinical Impact and Military Relevance: Through a carefully designed clinical trial, we hope to demonstrate the efficacy of prazosin as a treatment option for PTHA. If effective as a prophylactic agent, its use would reduce the need for abortive and/or analgesic drugs, many of which have unacceptable cognitive side effects, addictive potential, and a tendency to increase the risk for developing superimposed medication over-use headaches. Because of its beneficial effect on improving symptoms of PTSD and decreasing alcohol abuse, prazosin may provide multi-factorial treatment for commonly co-morbid conditions. Such efficacy will enhance SMs' and Veterans' work and interpersonal function, and improve their overall quality of life.

| ASC     | Anodyma Symptom Checkinst   |
|---------|---|
| AUDIT-C | Alcohol Use Disorders Identification Test – Consumption                     |
| BBB     | Blood Brain Barrier   |
| BMI     | Body Mass Index   |
| BP      | blood pressure  |
| BPH     | benign prostatic hypertrophy  |
| CBOC    | community-based outpatient clinic   |
| CDE     | Common Data Elements  |
| CES     | Combat Experiences Scale  |
| CIRO    | Clinical Investigation Research Office                                      |
| CNS     | central nervous system  |
| CoC     | Certificate of Confidentiality  |
| CRF     | case report form  |
| CSD-E   | Consensus Sleep Diary E   |
| CSF     | cerebrospinal fluid   |
| DAQ     | Data Access & Quality Committee   |
| DCI     | Department of Clinical Investigation  |
| DoD     | Department of Defense   |
| DSMB    | data safety monitoring board  |
| DSM-IV  | Diagnostic and Statistical Manual of Mental Disorders, 4th Edition          |
| DSM-5   | Diagnostic and Statistical Manual of Mental Disorders, 5th Edition          |
| DVA     | Department of Veterans Affairs  |
| DVBIC   | Defense and Veterans Brain Injury Center                                    |
| EHR     | Electronic Health Record  |
| EKG     | electrocardiogram   |
| ESS     | Epworth Sleepiness Scale  |
| FDA     | Food and Drug Administration  |
| FITBIR  | Federal Interagency Traumatic Brain Injury Research                         |
| GAO     | Government Accountability Office  |
| GUID    | Global Unique Identifier  |
| HA      | Headache  |
| HAM-D   | Hamilton Depression Rating Scale  |
| HIPAA   | Health Insurance Portability and Accountability Act of 1996                 |
| HIT-6   | Headache Impact Test 6  |
| HJF     | Henry M. Jackson Foundation for the Advancement of Military Medicine        |
| HR      | heart rate  |
| HRPO    | Human Research Protection Office  |
| ICC     | Interclass Correlation  |
| ICHD-2  | International Classification of Headache Disorders, 2 nd edition |
|         |   |

#### List of Abbreviations

American Congress of Rehabilitation Medicine

angiotensin converting enzyme

Allodynia Symptom Checklist

Adverse Events analysis of covariance

adrenoreceptor

analysis of variance

ACE

ACRM AEs

ANCOVA

ANOVA

AR

ASC

| ICHD-3 beta | International Classification of Headache Disorders, 3 rd edition (beta version) |
|-------------|--|
| IHS         | International Headache Society   |
| IND         | Investigational New Drug   |
| IRB         | Institutional Review Board   |
| ISI         | Insomnia Severity Index  |
| ITT         | Intent to Treat  |
| JBLM        | Joint Base Lewis-McChord   |
| LC          | locus coeruleus  |
| Madigan     | Madigan Army Medical Center  |
| MIDĂS       | Migraine Disability Assessment   |
| MIRECC      | Mental Illness Research, Education, and Clinical Center                                    |
| MoCA        | Montreal Cognitive Assessment  |
| MOH         | medication over-use headache   |
| MOS         | Military Occupational Specialties  |
| MP          | Military Police  |
| mTBI        | mild traumatic brain injury  |
| NA          | noradrenergic  |
| NE          | norepinephrine   |
| NINDS       | National Institute of Neurological Disorders and Stroke                                    |
| NSAID       | nonsteroidal anti-inflammatory drug  |
| NSI         | Neurobehavioral Symptom Inventory  |
| OEF         | Operation Enduring Freedom   |
| OHRP        | Office of Human Research Protections   |
| OIF         | Operation Iraqi Freedom  |
| OIG         | Office of the Inspector General  |
| OND         | Operation New Dawn   |
| ORO         | Office of Research Oversight   |
| PCL-5       | PTSD Checklist for DSM-5   |
| PHI         | Protected Health Information   |
| PHQ-9       | Patient Health Questionnaire-9   |
| PI          | Principal Investigator   |
| PRIME-MD    | Primary Care Evaluation of Mental Disorders  |
| prn         | pro re nata - as needed   |
| PSQI        | Pittsburgh Sleep Quality Index   |
| PTHA        | posttraumatic headache   |
| PTSD        | posttraumatic stress disorder  |
| qam         | each morning   |
| qhs         | each evening at bedtime  |
| R&DC        | Research and Development Committee   |
| RCT         | randomized controlled trial  |
| REM         | rapid eye movement   |
| Ret         | retired  |
| ROI         | Release of Information   |
| SAE         | Serious Adverse Event  |
| SCID-5      | Structured Clinical Interview for DSM-5  |
| SD          | standard deviation   |

| SE             | standard error of the mean                             |
|----------------|--|
| SF-36          | Short Form 36  |
| SIBCR          | Seattle Institute for Biomedical and Clinical Research |
| SM             | Service Member   |
| SSN            | social security number                                 |
| TBI            | traumatic brain injury                                 |
| UPSIS-12M      | Utah Photophobia Symptom Impact Scale-12-Modified      |
| US             | United States of America                               |
| USAMRMC        | U.S. Army Medical Research and Materiel Command        |
| VA Puget Sound | VA Puget Sound Health Care System                      |
| VA             | Veterans Affairs                                       |
| VISN-20        | Veterans Integrated Service Network 20                 |
| VR-12          | Veterans RAND 12                                       |
| VS             | vital signs  |
| WA             | Washington State                                       |
|                |  |

#### Introduction 2.0

**Overview:** Headaches (HAs) following combat-related mild traumatic brain injury (mTBI) are common, and can persist and worsen to become a debilitating chronic pain syndrome. These posttraumatic HAs (PTHAs), which often have migraine features, can be refractory to standard prophylactic treatment. Here, we propose a randomized controlled trial (RCT) to evaluate the medication prazosin as a prophylactic treatment for postconcussive PTHAs in active-duty Service Members (SMs) and Veterans at Madigan Army Medical Center/Joint Base Lewis-McChord (Madigan/JBLM) and Veterans at VA Puget Sound Health Care System (VA Puget Sound). Prazosin, a brain-active clinically available alpha-1 adrenoreceptor (AR) antagonist, has shown promise in preliminary studies for efficacy with good long-term tolerability and no addictive potential for prophylaxis of combat mTBI-related PTHAs in this population. An RCT to confirm these encouraging results is necessary to evaluate definitive prazosin efficacy for prophylaxis of frequent persistent PTHAs.

Persistent PTHA Following Concussion in Iraq/Afghanistan SMs and Veterans: An estimated 19% of Iraq/Afghanistan Veterans have sustained deployment-related mTBI, the majority of these cases the result of explosive blast concussive injury. Irrespective of the cause of injury, the prevalence of HAs associated with mTBI is high, ranging from 22% to 97%. While these PTHAs often resolve within a year, they may persist and worsen in frequency and severity, becoming treatment-refractory and leading to significant disability.

The International Classification of Headache Disorders, 3rd edition (beta version) (ICHD-3 beta) defines PTHA as a secondary HA syndrome precipitated by an inciting event of head, neck, or facial trauma, with onset occurring within 7 days of the trauma or within 7 days of regaining the capacity to perceive and report HA following the trauma. These time of onset criteria have been criticized as being arbitrary, and in practice onset of HAs within weeks or months of trauma with no other evident precipitating factors is often observed. HAs that continue for more than 3 months are defined by ICHD-3 beta criteria as being persistent (previously termed "chronic" in ICHD-2).

Clinically, HAs precipitated by trauma do not have unique defining characteristics and are treated empirically based on their resemblance to primary HA disorders. In the civilian TBI population, for whom injury is by far most often due to mechanisms other than blast, PTHAs tend to be tension-type, migraine, or mixed, whereas in the military combat population, particularly in the setting of blast TBI and physical injury, HAs with migraine features predominate. These blast-related PTHAs seem to be more refractory to standard prophylactic pharmacotherapies than those following non-blast TBI, as demonstrated in a retrospective cohort study evaluating medical treatments of PTHAs in SMs conducted by study Consultant, COL [name], at the Madigan Neurology Clinic. HA frequency was determined at initial clinic visit and again at 3 months after starting HA prophylactic medications. Only 29% of blast-TBI PTHA patients compared to 57% of non-blast TBI PTHA patients had a 50% or greater decline in HA frequency (P=0.023) with treatment. This reduced rate of response is concerning for an increased risk for development of long-term HA persistence (chronification). This concern is supported by findings from a recent cross-sectional study. Among 978 soldiers with deploymentrelated concussion, 20% met criteria for chronic daily HA (at least 15 HAs per month), which is 4- to 5fold higher than that seen in the general population. In this group, 66% had HA with migraine features. Chronic daily HA, particularly with migraine features, is considered to be one of the most disabling and difficult to treat HA syndromes.

HA disorders are one of the top reasons for military disability evaluation. Theeler et al found that migraine HAs tended to persist after return from deployment, and were associated with substantial disability. Seventy-seven percent of all migraine attacks interfered with duty performance on a mean of 2.4 days per month. Of particular concern is a recently reported association between migraine and suicide in Veterans. Based on a large-scale retrospective analysis of noncancer pain conditions and risk of suicide in Veterans, the investigators found a suicide mortality hazard ratio of 1.34 (1.02-1.77) for migraine, after controlling for comorbid psychiatric conditions.

Clearly, interventions are needed that will reduce the suffering and disability caused by frequent persistent PTHAs in the active-duty SM and Veteran populations. Successful management of persistent HAs can be a trial-and-error time-consuming process entailing substantial effort to optimize effective treatment for an individual patient. Even with careful management, HAs following mTBI often are treatment-refractory and difficult to control. Inadequate or inappropriate medication regimens used in attempts to preemptively abort impending HAs or treat HA pain can not only increase vulnerability to HA chronification, but can also lead to superimposed rebound or "medication over-use" HAs (MOHs) in some patients, particularly those with frequent HAs at baseline. MOHs occur in 19-42% of patients with PTHAs. The injudicious use of opioids is particularly problematic, with the added risk of opioid dependence. The role of effective prophylactic (preventive) agents is thus particularly important in reducing the need for abortive or analgesic treatment.

Preliminary data (see below) support prazosin as a rational candidate medication for PTHA prophylaxis. Prazosin has a well-characterized pharmacologic profile with minimal side effects, no major interactions with other medications, and no addictive potential, based on over 30 years of clinical experience since its Food and Drug Administration (FDA) approval. As previously noted, common co-morbidities in the combat head trauma population, notably PTSD, depression, and sleep disruption, may be coexistent conditions or may be contributory to HA genesis and/or exacerbation. A common physiologic substrate for these conditions may be over-activation of the central noradrenergic system, as suggested by their responsiveness to the centrally acting alpha-1 AR antagonist, prazosin.

Prazosin blocks alpha-1 ARs; it is the most lipid soluble of the alpha-1 AR antagonists, and it is the only one empirically demonstrated to cross the blood-brain barrier (BBB) to block norepinephrine (NE)

effects in the brain when administered peripherally. Prazosin was originally marketed as an antihypertensive agent and was subsequently found to be beneficial for treating benign prostatic hypertrophy (BPH). Project Principal Investigator (PI) [name], pioneered the use of prazosin for combat-trauma PTSD. He hypothesized that the noradrenergic (NA) hyperarousal adaptive in combat persisted and became maladaptive following return to civilian life, and further, that blocking postsynaptic alpha-1 ARs with prazosin would decrease NA hyperactivity. Based on this concept, prazosin was proposed as a potential treatment for PTSD and has since been shown in double-blind RCTs to relieve PTSD symptoms, including sleep disturbance and nightmares, and to improve global clinical status in Vietnam Veterans, in active-duty SMs and Veterans of Iraq and Afghanistan, and in civilians. In addition, prazosin has been found to reduce daytime hyperarousal symptoms of PTSD, including hypervigilance and irritability/anger.

[figure not shown]
**Prazosin Effects on Sleep and Actigraphic Monitoring of Sleep/Wake Activity:** We demonstrated that an important effect of prazosin treatment of PTSD is normalization of rapid eye movement (REM) sleep and an increase in total sleep time. Because improving sleep quantity and quality can be an important component of both migraine and PTHA prophylaxis, prazosin may be particularly helpful in treating persistent PTHA with its high prevalence of comorbid PTSD sleep disruption. In this study, we will monitor sleep/wake activity using wrist actigraphy (described in detail below). Studies have shown actigraphy correlates well with polysomnography in most sleep measures, including in a study of Iraq/Afghanistan Veterans with PTSD and mTBI.

**Current Status of the Field:** Currently available agents used for HA prophylaxis may be poorly tolerated and/or contraindicated for certain conditions; none of these agents are effective in all patients. For example, beta blockers are contraindicated in patients with bronchospasm, congestive heart failure, cardiac arrhythmias, or a history of depression. Tricyclic antidepressants may be sedating and are contraindicated in patients with some cardiac arrhythmias. Valproic acid causes weight gain, hair loss, and tremor, and its use may lead to hepatotoxicity, or rarely, pancreatitis. Topiramate has shown some benefit in reducing HA frequency in soldiers with PTHA, but it may cause sedation, decreased energy, and worsening of depression. More recently, onabotulinumtoxinA (Botox®) has shown efficacy for migraine prophylaxis in some patients, but this medication, like the others, has not been evaluated for PTHAs, and its effectiveness for chronic migraine prophylaxis, as for topiramate, is modest. A recent placebo-controlled trial assessing addition of propranolol to topiramate in treating chronic migraine HAs unresponsive to topiramate alone showed no evidence of benefit of combined therapy. Thus, there is an imperative for research to identify more effective treatment options.

Although practice guidelines for managing PTHAs following military-related TBI have been established by the Department of Defense (DoD) and Department of Veterans Affairs (DVA), recommended treatments have not been validated by RCTs in the active military SMs and Veteran population. This study is intended to address this need, with the express goal of providing a validated treatment option to a common refractory condition, and to do so in a timely manner. Anecdotal and case reports of the use of prazosin or other alpha-1 blockers for prophylaxis of HA have been identified in the literature; however, no Level I RCTs have been performed.

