# 5.0 Study Procedures

# 5.1 Study Design

**Overview:** The study is a prospective double-blind placebo-controlled RCT to evaluate the efficacy of prazosin for prophylactic treatment of frequent persistent HAs following blast and/or impact mTBI in a convenience sample of male and female SMs and Veterans aged 18 and older who have a history of mTBI with chronic PTHAs and who meet inclusion/exclusion criteria as described further below. We anticipate enrollment of 228 participants to achieve 160 randomized -- an average of approximately 4-5 participants randomized per month divided approximately equally across the 2 sites.

All study procedures are investigational; none are standard of care. The total trial length is up to 24 weeks, including a 5-week Preliminary Screening Period during which the participant will keep a HA log, eligibility for randomization will be determined, and baseline data (including 1 week of sleep/activity monitoring using actigraphy and keeping a sleep log) will be collected; a 5-7week Titration Period, during which optimal dose will be determined; and a 12-week Steady-Dose Period, as detailed in section 5.5 below and in the schedule of study visits table.

Participants who remain eligible after the Preliminary Screening period will be randomly assigned 2:1 to prazosin or placebo and will then begin the study drug dose Titration Period. During the Titration Period, the dose of study drug will be gradually increased to a maximum dose of 5 mg each morning and 20 mg each evening or to the maximum tolerated dose. Once the maximum (or maximum tolerated) dose has been attained, the participant will continue on this dose for 12 weeks. Evaluations to be performed are described in section 5.5 below and on the Schedule of Study Visits table.

**Investigational Drug:** This study will be conducted using the drug, prazosin, which has been approved by the FDA for treatment of hypertension but is being used off-label for investigational purposes in this study. Prazosin and indistinguishable placebo will be obtained from commercial sources. Investigational pharmacists at each study site will procure the study drug. Study drug may be stored at room temperature. Unused drug will be disposed of by the investigational pharmacists once notification has been made by the PI that the study has been completed.

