## 5.4 Inclusion/Exclusion Criteria

#### **Inclusion Criteria:**

- Male and female Active-duty SMs or Veterans aged 18 or older who are in good general health.
- History of blast and/or impact head trauma mTBI meeting Defense and Veterans Brain Injury Center (DVBIC) mTBI criteria.
  - Mild TBI is defined as an injury to the head causing at least one of the following: alteration in consciousness (for up to 24 hours after the injury), loss of consciousness (0-30 minutes), and/or post-traumatic amnesia (up to 1 day post-injury). If available, the Glasgow Coma Scale score must be 13-15, and head imaging findings (if imaging was performed) must be negative.
- Frequent HAs that started within 3 months after a head injury or marked worsening (a two-fold or greater increase in frequency and/or severity) of pre-existing headaches within 3 months of head injury.
  - HAs either 1) must last 4 or more hours a day and reach a moderate to severe intensity at any point during the headache, or 2) may be of any severity or duration if the participant takes a medication or other agent in an effort to stop or treat a headache.
  - HAs meeting these criteria must have been present on average at least 8 days per 4-week period, starting within 3 months after head injury and occurring at a stable level by self-report for at least 3 months prior to the Initial Screening Visit. The 4-week HA frequency/severity criteria must be confirmed during the Preliminary Screening Period.
- Participants of childbearing potential must agree to abstain from sexual relations that could result in pregnancy or use an effective method of birth control acceptable to both participant and the clinician prescriber during the study. Participants who not of childbearing potential are not required to use contraception during the study.
- Participants must have English fluency sufficient to complete study measures.

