Participants who fail screen for a reason that may change (e.g., stabilization of medications or treatment) may resume the screening process following stabilization. Previously collected information will be verified followed by resumption of headache logging for 4 weeks. Participants who screen fail for any reason may be rescreened if the reason for the screen fail has changed.

Randomization: before the Baseline Visit, participants will be randomized 2:1 to prazosin or placebo. Randomization will be stratified based on study site, gender, and whether participants meet the following criteria for medication overuse:

- 1. The regular use of ergotamine, triptans, opioids, or combination analgesics on 10 or more days during the Preliminary Screening Period. The term "combination analgesic" is used for formulations designed to treat migraine HAs that combine drugs of two or more classes, each with an analgesic effect or acting as adjuvants (e.g., Excedrin migraine, which contains aspirin, acetaminophen, and caffeine).
- 2. The regular use of individual "simple analgesics" (acetaminophen, aspirin, and other NSAIDS) on 15 more days during the Preliminary Screening Period.
- 3. The regular use of any combination of ergotamine, triptans, opioids, combination analgesics, and/or simple analgesics on 10 or more days during the Preliminary Screening Period, without over-use of any single drug or class alone.
- 4. Caffeine use of 300 mg or more on four or more days per week during the Preliminary Screening Period.

Titration Period (Baseline Visit and Study Drug Titration): At the Baseline Visit, medications will be reviewed, vital signs (BP and HR) will be checked to ensure absence of orthostatic hypotension, and a urine pregnancy test for women of child-bearing potential will be checked and must be negative. For participants who remain eligible for the study, measures will be performed as listed on the schedule of study visits. We will perform a short measurement of the pupillary light reflex. Participants will look into a device that uses an infrared camera to measure the diameter of the pupil at baseline and in response to very brief flashes of light. The measurements take approximately 30 seconds. Including set up and instructions to the participant, the procedure will take approximately two minutes. Blood (approximately 65 ml) will be collected from VA Puget Sound participants only for measurement of potential biomarkers related to headache

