Neurobehavioral Symptom Inventory (NSI): A 28-item self-report questionnaire designed to assess the presence and severity of common cognitive, emotional, sensory, and somatic symptoms that can occur after traumatic brain injury. It is widely used in VA hospitals across the country as part of the TBI Second Level Evaluation.

TBI History Interview: An 11-item questionnaire that characterizes the participant's traumatic brain injury exposures. Explosion/blast, impact and lifetime injuries are assessed. Dates associated with first TBI, most recent TBI and onset of headaches are captured.

Utah Photophobia Symptom Impact Scale-12-Modified (UPSIS-12M): A 12-item self-administered questionnaire designed to evaluate light sensitivity severity during and between headache attacks, light as a headache trigger, and the impact of light sensitivity on activities of daily living. The UPSIS was

developed with the intention of providing a quantitative tool for assessing effectiveness of treatment interventions. The UPSIS-12 has been validated for internal consistency and reliability against the 17-item UPSIS, the 8-item Korean Photophobia Questionnaire, which emphasizes photophobia only during headaches, and against quantitative psychophysical assessment of light sensitivity thresholds. Minor modifications tailored to the needs of this study have been made and discussed with the UPSIS developers.

| Visits   |
|----------|
| Study    |
| of       |
| Schedule |

|  |                      | Prel           | Preliminary Screening Period | Period         |                                 | F        | Titration Period b | ď b        |          | Stead               | Steady-dose Period  | p              |                 |
|--|----------------------|----------------|------------------------------|----------------|---------------------------------|----------|-------------------------------|-----------------------|----------|---------------------|---------------------|----------------|-----------------|
| Visit type   | Initial
Screening | Phone
Check | Review
Headache Log       | Phone
Check | Final
Screening a | Baseline | Standard
Titration         | Optional
Titration | Safety   | Safety/
Efficacy | Safety/
Efficacy | Phone
Check | End of
Study |

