**Statistical Analysis:** We will use summary statistics and graphs (e.g., strip charts, box plots, bar charts, scatter plots) to compare subject demographics at baseline by assigned treatment group (prazosin vs. placebo), and to initially compare outcomes by treatment group. Analyses will follow the intent to treat (ITT) principle. We will use a linear mixed effects model for the analysis of the primary outcome: 4-week frequency of moderate or severe HAs (Hypothesis 1a). We will have 4-week measures at four times during the course of the study: at Baseline, and at three different time points post-randomization (after 4, 8, and 12 weeks of steady-dose study drug). The response (dependent) variable will be 4-week frequency of moderate or severe HAs, and the predictor (explanatory) variables will include treatment group, week and a treatment group by week interaction term, along with the covariates site, gender, baseline age, baseline PSQI, time since onset of PTHAs, and analgesic use. A significant treatment group by week interaction term will indicate a significant difference in change from baseline between treatment groups. Results will include p-values, confidence intervals for change from baseline within each group, the confidence interval for difference in change from baseline between the two groups, and effect sizes.

We will also use linear mixed effects models for the secondary outcomes for Hypothesis 1b, i.e., 4-week average of: HA severity, number of hours of moderate to severe HA, individual HA duration, frequency of migraine days, frequency of non-migraine days, and frequency of use of abortive/analgesic medications (all obtained from the HA log); and for degree of HA-related disability (MIDAS and HIT-6). As for the primary outcome, secondary outcomes obtained from the HA log and the HIT-6 will have observations at four time points during the course of the study: Baseline and after 4, 8, and 12 weeks of steady-dose study drug; MIDAS will have observations at Baseline and week 12. The response (dependent) variable will be the secondary outcome, and the predictor (explanatory) variables will be the same as for the primary outcome.

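### Blast exposure is a plausible prognostic factor recorded before randomisation; adding it to the primary model in a form that acts on change would be a low-cost gain in precision

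*Combined protocol and SAP*

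**What the plan says.** Section 2.0 (Introduction) says that blast-related headaches "seem to be more refractory to standard prophylactic pharmacotherapies than those following non-blast TBI". It supports this with a retrospective cohort at the neurology clinic of one of the two trial sites: "Only 29% of blast-TBI PTHA patients compared to 57% of non-blast TBI PTHA patients had a 50% or greater decline in HA frequency", P=0.023, measured 3 months after prophylaxis began.

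The trial admits both mechanisms. Section 5.4 asks for "History of blast and/or impact head trauma mTBI meeting Defense and Veterans Brain Injury Center (DVBIC) mTBI criteria".

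Mechanism is recorded. The TBI History Interview is described in Section 5.5 with the words "Explosion/blast, impact and lifetime injuries are assessed", and the Schedule of Study Visits places TBI history at visit P1, before randomisation.

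Mechanism is not used in the design or the analysis. Section 5.5 states: "Randomization will be stratified based on study site, gender, and whether participants meet the following criteria for medication overuse". The primary model in Section 5.6 contains treatment, week and treatment-by-week, "along with the covariates site, gender, baseline age, baseline PSQI, time since onset of PTHAs, and analgesic use". The secondary outcomes use the same list, without baseline PSQI for the sleep outcomes. No analysis by mechanism is planned.

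**The concern.** The cohort's outcome, a fall in headache frequency on preventive treatment, is close to the trial's primary outcome, and the patients came from one of the trial's own sites. If mechanism predicts change in this trial too, leaving it out of the model puts that variation into the residual error of the treatment comparison, although the value is in hand before randomisation.

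The form of the term also matters. The primary model treats baseline as one of the four responses and tests treatment-by-week. The listed covariates carry no by-week term. A blast term simply added to that list would shift a participant's level at all four times equally, and would not account for any of the change.

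Precision is at stake, and with it a planned look at consistency. The document reports poor response of blast headaches to standard drugs and, separately, high response to open-label prazosin, but plans nothing that would show which pattern holds here.

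**Working it through.** **Inputs.** Response rates of 29% and 57% with P=0.023 (Section 2.0); 74 and 37 completers, effect size 0.57, two-sided 5% (Section 5.6). The documents do not give the blast share p, so 20-80% is assumed.

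**1. The plan's own figure.** SE = √(1/74 + 1/37) = 0.201 SD. Noncentrality = 0.57/0.201 = 2.83 on 109 degrees of freedom. Power = 80.1%, so the stated 80% is reproduced.

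**2. Size of the cohort gap.** Ratio: 0.29/0.57 = 0.51. On a latent normal scale, d = z(0.57) − z(0.29) = 0.176 − (−0.553) = 0.73 within-group SD. This assumes that a gap in the share with at least a 50% relative fall translates into SDs of change in headache days.

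**3. Share of variance explained.** R² = p(1−p)d² / [1 + p(1−p)d²], with d² = 0.533.
- p = 0.2 or 0.8: 0.085/1.085 = 0.079.
- p = 0.5: 0.133/1.133 = 0.117.

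**4. Power after adjustment.** The effective effect size is 0.57/√(1−R²).

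| Gap d | R² (p = 20-80%) | Power, 74/37 |
|---|---|---|
| 0.73 | 8-12% | 83-85% |
| 0.365 (half) | 2-3% | about 81% |
| 0.10 | about 0.2% | about 80% |

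The last row is not arbitrary. P=0.023 corresponds to |z| = 2.27, so the SE of d is about 0.73/2.27 = 0.32 and its 95% interval is 0.73 ± 1.96 × 0.32, about 0.10 to 1.36. The cohort alone is compatible with almost no gain and with a larger gain than the central row.

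**5. Chance imbalance.** The SD of the difference in blast share between arms is √[p(1−p)(1/74 + 1/37)], which is 8-10 percentage points. Multiplied by 0.73, this shifts the unadjusted estimate by 0.06-0.07 SD, about a third of its standard error of 0.20 SD (0.06/0.20 = 0.3; 0.07/0.20 = 0.35).

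**6. Form of the term.** In a simulation of 111 complete cases (74/37) at four time points, with blast reducing response, a time-constant blast term left the week-12 treatment contrast at −2.146 (SE 0.886), the same as without it. Blast-by-week moved the contrast to −2.425 and its SE to 0.836. The values depend on the simulated inputs. That a main effect changes nothing with complete data is structural: it cancels from every within-person change. With dropout the cancellation is only approximate.

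**7. What a look by mechanism can show.** At a 50% blast share, each subgroup has about 37 and 18.5 completers, with SE √(1/37 + 1/18.5) = 0.285. An effect of 0.57 within one subgroup then has about 50% power. The interaction has SE √2 × 0.285 = 0.403. An interaction as large as 0.57 gives 0.57/0.403 = 1.4 standard errors, about 29% power.

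**The case against.** The strongest reply is that nothing in the plan is invalid. Allocation is random ("randomly assigned 2:1 to prazosin or placebo"), there are already three stratification factors and six covariates, and no model includes every plausible predictor. The chance imbalance in step 5 is part of the sampling variation that the confidence interval and the 5% error rate already cover. All of this stands, and it is why the point is an improvement only.

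The evidence is also indirect. The cohort is retrospective, has no placebo arm and concerns standard drugs. A reader might infer that blast patients will respond poorly to prazosin and dilute the trial. If blast halved the treatment effect, the average effect at a 30-80% blast share would be 0.49 down to 0.35, and power 67% down to 40%. The documents do not support that assumption. Under Preliminary Studies, Section 2.0 reports that more than three quarters of 74 Veterans with blast-related headache had more than a 50% fall in frequency on open-label prazosin with sleep hygiene counselling. That series is uncontrolled too, but it points the other way.

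A reader might also infer that a negative result could not be told apart from a sample heavy in blast injury. It could be examined, because mechanism is recorded and can be tabulated. Nor is blast the only factor with support in the text: Section 2.0 also says that headaches persisting over time may become treatment-refractory, which gives time since onset a rationale, though no figure.

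Finally, since "History of blast and/or impact head trauma mTBI" qualifies, some participants will have had both mechanisms, and the injury that started the headaches may not be the blast. A simple blast variable may not reproduce the cohort's split. That caution stands.

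**Conclusion.** The point holds as a low-cost improvement. The cohort makes blast a plausible prognostic factor, the value is available before randomisation, and the primary model does not use it. The planned comparison remains valid without it, so the loss is one of modest precision: power of 80% instead of about 83-85% if the cohort gap carries over in full, about 81% if half of it does, and essentially no difference near 0.1 SD. These figures rest on the latent-scale conversion, on transfer of a gap seen with standard prophylactics to change in this trial, and on an assumed blast share of 20-80%. The documents do not establish that blast modifies the effect of prazosin, and the trial is too small to test that well.

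**What to change.** In Section 5.6:

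- Define the variable in advance as any blast mTBI versus impact only, from the TBI History Interview at P1, and say how participants with both mechanisms are classed.
- Enter it in the primary model as blast-by-week, or as a covariate in a baseline-adjusted model. Do not simply append it to the existing list of main effects.
- Report the treatment difference with its confidence interval separately by mechanism, labelled as descriptive.

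Leave the stratification as it is. Site, gender and medication overuse already make 2 × 2 × 2 = 8 cells for 160 participants, and a fourth factor could leave some of them sparse.

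The cost is a few sentences and 1-3 degrees of freedom. No new data and no change in sample size are needed. The remaining downside is that the chosen definition may not match the cohort's, in which case the gain will be smaller.
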